## 1. Synopsis

**Title of Study:**

A Multicenter, Open-Label, Single-Arm, Phase 4 Study to Assess the Safety of Basaglar in Subjects with Type 2 Diabetes Mellitus in India

**Rationale:**

Basaglar® (LY2963016; Eli Lilly and Company [Lilly], Indianapolis, IN, USA, and Boehringer Ingelheim, Ingelheim Rheim, Germany) is an insulin glargine product which received marketing approval in India in 2017 as a biosimilar of LANTUS® (Sanofi Aventis, Paris, France) insulin glargine. It is approved for the treatment of patients with type 1 and type 2 diabetes mellitus (T2DM) above 2 years of age. As a clause towards marketing approval, the Drug Controller General of India, in accordance to the biosimilar guidelines for India, recommended that Basaglar be studied in a minimum of 200 additional local subjects without specific guidance towards objective of the study from an efficacy or safety perspective.

Patients with T2DM who are unable to meet glycemic targets in spite of being on oral antihyperglycemic medications and/or glucagon-like peptide-1 receptor agonist and need to initiate basal insulin, are usually preferred for treatment with Basaglar. Hence, it was decided to conduct the study in these patients. The efficacy of the drug is well established based on results from 3 randomized controlled trials in patients with type 1 diabetes and T2DM. In this study, we would seek to understand the safety of this drug in the local Indian population in accordance with the biosimilar guidelines of India.

**Objectives/Endpoints:**

Objectives	Endpoints
Primary 
 
To assess risk of hypoglycemia in adult subjects with T2DM in India who will be administered Basaglar
 
	
 
Incidence of total (symptomatic or asymptomatic, with FBG level <math>\leq 54</math> mg/dL [3.0 mmol/L]) hypoglycemic events at Week 24
 

Secondary 
 
To assess adverse events and other safety parameters in adult subjects with T2DM in India
 
To assess efficacy of Basaglar in adult subjects with T2DM in India
 
To assess outcomes reported by adult subjects with T2DM in India
 
	
 
SAEs and TEAEs
 
Rates per 30 days and per subject year of total (symptomatic or asymptomatic) hypoglycemic events
 
Incidence and rates per 30 days and per subject-year of nocturnal, severe, documented symptomatic and asymptomatic hypoglycemic events
 
Basal insulin dose (U/day and U/kg/day)
 
Change in weight and BMI at Week 24 from baseline
 
Change in HbA1c at Week 12 and Week 24 from baseline
 
Percentage of subjects reaching HbA1c targets <math>\leq 6.5\%</math> or <math>< 7\%</math>
 
Change in FBG levels at Weeks 4, 8, and 12 from baseline
 
Self-monitored 7-point SMBG levels at baseline, Weeks 4, 8, 12, and 24
 
Change in 7-point SMBG levels at Weeks 4, 8, 12, and 24 from baseline
 
Intrasubject variability, as measured by SD of 7-point SMBG levels
 
Change in Insulin Treatment Satisfaction Questionnaire score at Week 24 from Week 4
 

Abbreviations: BMI = body mass index; FBG = fasting blood glucose; HbA1c = glycated hemoglobin;

SAE = serious adverse event; SD = standard deviation; T2DM = type 2 diabetes mellitus; TEAE = treatment-emergent adverse event; SMBG = self-monitored blood glucose.

**Summary of Study Design:**

Study I4L-IN-ABEX is a multicenter, open-label, single-arm study, that will enroll insulin-naïve subjects with T2DM. The study period consists of a screening period (Week -2 to Week 0), a treatment period (Week 0 to Week 24), and a safety follow-up visit at Week 28.

**Treatment Arms:**

This is a single-arm study. Enrolled subjects will be treated with Basaglar using a self-titration scheme as outlined below.

Fasting Blood Glucose (mg/dL)	Fasting Blood Glucose (mmol/L)	Dose Adjustments (Units)
<80	<4.4	-2
80-100	4.4-5.6	0
101-130	5.6-7.2	+2
131-160	7.3-8.9	+4
161-190	8.9-10.6	+6
>190	>10.6	+8

### Number of Subjects:

Indian regulatory authorities have recommended the study to be done in a minimum of 200 local subjects. Assuming a 15% screen failure rate, approximately 295 subjects will be screened, so that 250 subjects can be enrolled. Assuming a drop-out rate of 20%, the target is to have a minimum of 200 subjects completing the present study.

In the India subpopulation of ELEMENT 5 study, 5 of the 46 insulin-naïve subjects experienced at least 1 hypoglycemic event (total hypoglycemia incidence with glucose levels  $\leq 54$  mg/dL [3.0 mmol/L]) during the overall study period. When considering the total ELEMENT 5 population, 146 out of 489 subjects (30%) experienced at least 1 hypoglycemic event during the overall study period. Based on these estimates, the precision with 250 and 200 subjects would be as follows (95% confidence interval for proportion shown based on normality assumption):

Sample Size	Estimated Proportion	Standard Error	Width of Proportion to 95% Confidence Limit	Width of Interval (2 Sides)	95% Lower Confidence Limit	95% Upper Confidence Limit
250	11%	2.0%	3.9%	7.80%	7.1%	14.9%
250	30%	2.9%	5.7%	11.40%	24.3%	35.7%
200	11%	2.2%	4.3%	8.60%	6.7%	15.3%
200	30%	3.2%	6.4%	12.80%	23.6%	36.4%

### Statistical Analysis:

No randomization will be performed as this is a single-arm study. The sample size was calculated assuming a 15% screen failure rate, with a target to have a minimum of 200 subjects completing the study. No interim analyses and/or sample size re-estimation are planned to be performed.

Statistical Methodology:

Primary endpoint: Incidence of the total (symptomatic and asymptomatic) hypoglycemic events at Week 24 will be assessed as number and percentage of subjects experiencing at least 1 event over the study period.

Secondary outcomes: Actual values and change in glycated hemoglobin (HbA1c) level from baseline to Week 12 and Week 24 will be analyzed in a descriptive manner on non-missing values and last observation carried forward-imputed values. Additionally, a general linear model will be performed on the full analysis set (FAS), with change from baseline in HbA1c level as the dependent variable and the baseline value of HbA1c as a covariate.

The number of hypoglycemic events per subject, the rate of hypoglycemic events per 30 days, and the rate per year, that is, the number of hypoglycemic events per subject year (365.25 days) will be assessed using a negative binomial model, with baseline HbA1c as a covariate and the log of the study treatment exposure time as an offset variable.

The analysis for other continuous secondary efficacy and safety measurements and continuous laboratory measures will use the general linear model for the FAS population with the baseline value of the response variable as a covariate.

## 2. Schedule of Activities

**Table ABEX.1. Schedule of Activities**

Procedure	Screening	Treatment Period							Follow-up	Notes
Visit	1	2	3	4	5	6a	7a	8	9/ET	
Week of Study	-2	0	4	8	12	16	20	24	28	
Allowable Deviation +/- (days)		3	7	7	7	7	7	7		
Informed consent	X									
Subject number assigned	X									
Inclusion and exclusion criteria	X									
Clinical Assessments										
Demography	X									
Full physical examination	X									
Height and weight	X	X						X		Height will be measured only at screening.
Vital signs b	X	X	X	X	X			X	X	SBP, DBP, and PR
Medical history and family history of CV disease	X									
History of substance usage	X									Substances: drugs, alcohol, tobacco, and caffeine
12-lead ECG	X									To be recorded in a resting supine state
Concomitant medication review	X	X	X	X	X	X	X	X	X	
AE/SAE/complaint handling		X	X	X	X	X	X	X	X	
Hypoglycemic events		X	X	X	X	X	X	X	X	
Completion or discontinuation of investigation			X	X	X	X	X	X	X	
FBG c		X	X	X	X					

Procedure	Screening	Treatment Period							Follow-up	Notes
Visit	1	2	3	4	5	6 a	7 a	8	9/ET	
Week of Study	-2	0	4	8	12	16	20	24	28	
Allowable Deviation +/- (days)		3	7	7	7	7	7	7		
7-point SMBG measurement d		X	X	X	X			X		
Laboratory Assessments										
Hematology, clinical chemistry, and urinalysis tests	X				X			X		See Appendix 2 for details. Estimated glomerular filtration rate will be measured only in subjects with a history of severe chronic kidney disease.
Pregnancy test (for WCBP only)	X	X								Serum pregnancy test at Visit 1 and urine pregnancy test at Visit 2 prior to being given the study drug
HIV, hepatitis B and C	X									
HbA1c measurement	X	X			X			X		
Subject-reported outcomes										
ITSQ			X					X		
Ancillary Supplies/Diaries/Study Drug										
Trainings on signs/symptoms of hypo/hyperglycemia and insulin reactions		X	X	X	X	X	X	X		This training is given at baseline and reinforced at every visit of the treatment period
Trainings on injection technique, use of glucometer and 7-point SMBG measurement	X	X	X	X	X			X		This training is given during screening and reinforced at every face-to-face visit of the treatment period

Procedure	Screening	Treatment Period							Follow-up	Notes
Visit	1	2	3	4	5	6 a	7 a	8	9/ET	
Week of Study	-2	0	4	8	12	16	20	24	28	
Allowable Deviation +/- (days)		3	7	7	7	7	7	7		
Self-titration training c		X	X	X	X	X	X	X		This training is given at baseline and reinforced at every visit of the treatment period
Dispense study diary	X	X								Pretreatment study diary will be dispensed at Visit 1 and comprehensive study diary will be dispensed at Visit 2
Dispense study drug		X	X	X	X					
Review study diary		X	X	X	X			X		Pretreatment study diary will be collected at Visit 2 and comprehensive study diary will be collected at Visit 8
Collect unused study drug			X	X	X			X		
Dispense glucometer	X									
Compliance to study drug administration		X	X	X	X	X	X	X		
Adjust insulin dose (if required)			X	X	X			X		Site personnel will review the Basaglar dose and FBG levels recorded in the subject diary. They may recommend change in dose of Basaglar if required.

Abbreviations: AE = adverse event; CV = cardiovascular; DBP = diastolic blood pressure; ECG = electrocardiogram; ET = early termination; FBG = fasting blood glucose; HbA1c = glycated hemoglobin; HIV = human immunodeficiency virus; ITSQ = Insulin Treatment Satisfaction Questionnaire; PR = pulse rate; SAE = serious adverse event; SBP = systolic blood pressure; SMBG = self-monitored blood glucose; WCBP = women of child-bearing potential.

- a Telephone visit.
- b All vital signs should be recorded in the subject in a resting state. If there is a suspicion of postural hypotension or autonomic instability, the investigators at their discretion might decide to record the blood pressure in a supine state and then after standing for 2 minutes to detect any postural hypotension. Blood pressure measurements should be done in the left arm with sphygmomanometer held at the level of the heart. Blood pressure recording in both arms is at the investigators' discretion in selective cases of pulse volume inequality or pulse being absent in either of the arms.
- c Subjects will be instructed to daily measure the FBG levels mandatorily using glucometer before the morning meal till Week 12 and record in the subject diary. Also, subjects will be instructed to measure and record the blood glucose levels using glucometer if they have symptoms of hypoglycemia (including nocturnal hypoglycemia) at any time of the day or night.
- d Subjects will be instructed to perform 7-point SMBG level monitoring (glucose measurements before breakfast, lunch, and dinner; 2 hours after breakfast, lunch, and dinner; and at 3 am [ $\pm$  1 hour]) 2-3 days in the week prior to Visits 2, 3, 4, 5, and 8, and record the values in the subject diary. Subjects will be instructed to carry the glucometers to the sites on Visits 2, 3, 4, 5, and 8.
- e Subjects will be instructed to record the actual time and dose of Basaglar administration in the subject diary.

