### 6.2. Exclusion Criteria

Subjects will be excluded from study enrollment if they meet any of the following criteria at screening:

- [7] have any form of diabetes other than T2DM
- [8] have hypersensitivity to the active substance of Basaglar or to any of the excipients
- [9] have any clinically significant disorder, other than T2DM, that in the investigator's opinion, would preclude participation in the trial
- [10] are receiving systemic glucocorticosteroids therapy or have excessive insulin resistance (total insulin dose  $> 2$  U/kg)
- [11] have a history or diagnosis of human immunodeficiency virus infection, hepatitis B and C
- [12] have comorbidities of unstable angina, cardiac failure (Stage III or IV as per New York Heart Association guidelines) or renal failure (estimated glomerular filtration rate  $< 30$  mL/min/m^2)
- [13] are pregnant or intend to become pregnant during the course of the study; or are sexually active women of child-bearing potential not actively practicing birth control by a medically acceptable method as determined by the investigator
- [14] is a woman who is breastfeeding
- [15] are investigator site personnel directly affiliated with this study and/or their immediate families. Immediate family is defined as spouse, parent, child, or sibling, whether biological or legally adopted
- [16] are Lilly employees or are employees of third party organizations involved in the study who require exclusion of their employees

- [17]have participated within the last 30 days in a clinical trial involving an investigational product other than the Basaglar. If the previous investigational product has a long half-life, 3 months or 5 half-lives (whichever is longer) should have passed
- [18]have previously completed or withdrawn from this study or any other study investigating Basaglar. This exclusion criterion does not apply to subjects who are rescreened prior to baseline visit
- [19]are currently enrolled in any other clinical study involving an investigational product or any other type of medical research judged not to be scientifically or medically compatible with this study
- [20]are unwilling or unable to comply with the use of a glucometer

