**Pregnancy Test (females only)e**

Abbreviations: CRO = contract research organization; RBC = red blood cell; WBC = white blood cell.

a Assayed by CRO-designated laboratory agreed by Lilly.

b Screening visit (Week -2) and Week 24 results will be confirmed by the Central Laboratory.

c Refer to the Schedule of Activities: Abbreviated chemistry includes total bilirubin, direct bilirubin, ALT, BUN, and serum creatinine.

d Estimated glomerular filtration rate may also be measured but only in subjects with a history of severe chronic kidney disease

e Local- or investigator-designated laboratory.

---

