4.2 Schedule of events

The schedule of evaluations and procedures to be performed at specific time points is described in the following table 4.2.

| Procedure | Screening | | | Tre | eatme | ent Pe | eriod | | Follow-up | Notes | |
|--|-----------|---|---|-----|-------|----------------|-----------------------|----|-----------|---|--|
| Visit | 1 | 2 | 3 | 4 | 5 | 6 ^a | 7 ^a | 8 | 9/ET | | |
| Week of Study | -2 | 0 | 4 | 8 | 12 | 16 | 20 | 24 | 28 | | |
| Allowable Deviation +/- (days) | | 3 | 7 | 7 | 7 | 7 | 7 | 7 | | | |
| Informed consent | X | | | | | | | | | | |
| Subject number assigned | Х | | | | | | | | | | |
| Inclusion and exclusion criteria | | | | | | | | | | | |
| Clinical Assessments | | | | | | | | | | | |
| Demography | X | | | | | | | | | | |
| Full physical examination | X | | | | | | | | | | |
| Height and weight | X | X | | | | | | X | | Height will be measured only at screening. | |
| Vital signs ^b | X | X | X | X | Х | | | X | X | SBP, DBP, and PR | |
| Medical history and family history of CV disease | X | | | | | | | | | | |
| History of substance usage | Х | X | X | X | Х | X | X | X | | Substances: drugs, alcohol, tobacco, and caffeine | |
| 12-lead ECG | X | | | | | | | | | To be recorded in a resting supine State | |
| Concomitant medication review | X | X | X | X | Х | X | X | X | X | | |
| AE/SAE/complaint handling | | X | X | X | Х | X | X | X | X | | |
| Hypoglycemic events | | X | X | X | Х | Х | X | X | X | | |
| Completion or discontinuation of investigation | | | × | | Х | X | X | X | X X | | |
| FBG ^c | | X | X | X | Х | | | | | | |
| 7-point SMBG measurement ^d | | X | × | X | X | | | X | | | |
| Laboratory Assessments | | | | | | | | | | | |

Table 4.2

CONFIDENTIAL

Page 14 of 85

CS.BS.01.00 TPL-1.0: Statistical Analysis Plan Template

| Hematology, clinical chemistry, and urinalysis tests | X | | | | X | | | X | | See Appendix 2 of protocol for details. Estimated glomerular filtration rate will be measured only in subjects with a history of severe |
|---|---------------------------|---|---|----|------|----------------|----------------|----|-------------------|--|
| Procedure | Screening | - | | Tr | eatm | ent P | ariad | | Followur | chronic kidney disease. |
| Visit | 1 | 2 | 3 | 4 | 5 | 6 ^a | 7 ^a | 8 | Follow-up 9/ET | Notes |
| Week of Study | -2 | 0 | 4 | | 12 | 16 | 20 | 24 | 28 | |
| Allowable Deviation +/- (days) | | 3 | 7 | 7 | 7 | 7 | 7 | 7 | 20 | |

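### Exclusion [12] applies an eGFR threshold to every subject at screening, but the plan provides an eGFR only for subjects with known severe chronic kidney disease

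*Protocol*

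**What the plan says.** **The criterion.** Protocol Section 6.2 opens: "Subjects will be excluded from study enrollment if they meet any of the following criteria at screening". Exclusion [12] then lists, among other conditions, "renal failure (estimated glomerular filtration rate" below 30). It is a numeric threshold with no stated limitation to subjects already known to have kidney disease.

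**The measurement.** Three places say who gets an eGFR:

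- Protocol Section 2, Table ABEX.1, laboratory row: "Estimated glomerular filtration rate will be measured only in subjects with a history of severe chronic kidney disease".
- SAP Section 4.2, Table 4.2, same row: "Estimated glomerular filtration rate will be measured only in subjects with a history of severe" chronic kidney disease.
- Protocol Appendix 2, footnote d: "Estimated glomerular filtration rate may also be measured but only in subjects with a history of severe chronic kidney disease". This footnote is attached to the urinalysis panel, not the chemistry panel.

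**Other renal data.** The row "Hematology, clinical chemistry, and urinalysis tests" is marked for all subjects at Visit 1, Week 12 and Week 24. The Appendix 2 chemistry panel includes creatinine and blood urea nitrogen, and the urinalysis panel includes protein. The reduced panel keeps both blood markers: "Abbreviated chemistry includes total bilirubin, direct bilirubin, ALT, BUN, and serum creatinine". eGFR itself is not an item in any Appendix 2 panel, nor among the laboratory parameters in SAP Section 17.1.

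**Where eligibility feeds the analysis.** Protocol Section 10.2 and SAP Section 6.3 both require that per-protocol subjects have no inclusion or exclusion violations. The SAP implements this through recorded major deviations.

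**The concern.** A numeric exclusion can only be applied where the number is available. Here the number is planned for subjects whose severe kidney disease is already on record, and not for those in whom a low value would be news.

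Three things in the protocol depend on the criterion working:

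- Section 6.2.1 groups [12] with the exclusions meant to prevent effects not attributable to the regimen or misinterpretation of results.
- Section 6 forbids eligibility waivers, and Section 8.1.3 sets out what happens to subjects enrolled inadvertently. Both presuppose that a violation is noticed.
- The per-protocol set removes eligibility violators. An eGFR that is never derived generates no deviation record, so the subject stays in.

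The primary objective is hypoglycemia risk under self-titrated insulin, so the protocol's own safety exclusions should be applied in the same way at every site.

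**Working it through.** The plan gives no figure to reproduce. The check is a comparison of texts.

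| Question | Protocol 6.2, [12] | Protocol Table ABEX.1 | SAP Table 4.2 | Protocol Appendix 2, note d |
|---|---|---|---|---|
| Who? | All subjects | Known severe kidney disease only | Known severe kidney disease only | Known severe kidney disease only |
| Obligation | Must exclude if below 30 | Will be measured | Will be measured | May be measured |
| Equation or creatinine cut-off | None | None | None | None |

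1. **Is [12] limited to known disease?** Not in its wording. Exclusion [11], just above it, is framed as a history or diagnosis. Exclusion [12] instead gives a value to be met at screening.
2. **Is eGFR available for everyone?** No. The Schedule and the SAP restrict it to one subset. Footnote d does not guarantee it even there, which conflicts with the Schedule.
3. **Could it be obtained from what is collected?** Yes. Creatinine is measured at Visit 1 in all subjects. Age and sex come from demography. SAP Section 11.1 derives age from year of birth with 1 July imputed, so age is accurate to about half a year.
4. **Does any text instruct this?** No. Neither document tells sites or the laboratory to make the calculation.
5. **Consequence.** As written, [12] is applied by eGFR at most to subjects with known severe kidney disease. For the rest, per-protocol criterion (a) cannot be confirmed from planned eGFR data.

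**Effect on the primary estimate, as a bound only.** The documents give no prevalence of unrecognised eGFR below 30. Suppose *k* such subjects are among 250, all have an event, and the others have the planning incidence of 11% (Protocol Section 5.2). Then:

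shift = [*k* × 1 + (250 − *k*) × 0.11] / 250 − 0.11 = 0.89*k* / 250

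- *k* = 1: 0.89 / 250 = 0.0036, about 0.4 percentage points.
- *k* = 5: 4.45 / 250 = 0.0178, about 1.8 percentage points.

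The planned half-width at this incidence is 3.9 points (Table ABEX.3; 1.96 × √(0.11 × 0.89 / 250) = 0.0388). The values of *k* are illustrative. They correspond roughly to an assumed prevalence of 0.5% to 2% (250 × 0.005 = 1.25; 250 × 0.02 = 5) with none detected by other means.

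**The case against.** The strongest reply is that renal function is in fact screened in everyone. Creatinine, blood urea nitrogen and urinary protein are measured at Visit 1, and Appendix 2 footnote b has screening results confirmed centrally. Section 9.2 requires investigators to document review of each laboratory safety report. Medical history and a full physical examination are also taken, and exclusion [9] lets the investigator exclude any other significant disorder. This stands. A reader might infer that undiagnosed renal failure cannot be excluded at all, and the documents do not support that. What they lack is the step from creatinine to the criterion's own scale. Exclusion [9] does not supply it, because it rests on opinion and [12] on a number.

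A reader might also infer that the plan forbids calculating eGFR in other subjects. It does not say so. It limits who has eGFR measured and is silent on deriving it from creatinine. Attaching footnote d to urinalysis adds to the ambiguity.

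A charitable reading is that [12], which speaks of comorbidities, means documented renal failure only. That would fit the Schedule, but the criterion does not say it, and the conflict between will and may would remain.

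Finally, Protocol Section 10.3.1 conducts the safety and efficacy analyses on the full analysis or safety set, whose definition does not depend on eligibility. The per-protocol analysis is a repeat. Stored creatinine would also allow a retrospective check. Both points stand and limit the statistical consequence.

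**Conclusion.** The inconsistency is real and rests on the text alone. Exclusion [12] is set for all subjects, eGFR is planned for a subset, and the documents disagree on whether it is mandatory even there. The criterion is not put into operation for subjects without known severe kidney disease, and per-protocol criterion (a) cannot be verified for it from planned eGFR data.

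The number affected cannot be estimated from the documents. A reader might take 1 to 5 of 250 as the expected number wrongly enrolled. That range needs an assumed prevalence, and it also assumes that creatinine, investigator review and exclusion [9] detect nobody. Even on those terms and with every such subject having an event, the primary incidence moves by about 0.4 to 1.8 points, less than the planned half-width.

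The point therefore concerns consistent eligibility checking and subject safety rather than the validity of the primary analysis. It should be corrected because the remedy is specific and cheap.

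**What to change.** Reconcile four places: exclusion [12] in Protocol Section 6.2, the laboratory note in Table ABEX.1, footnote d in Appendix 2, and SAP Table 4.2. The result should be that [12] is checked as written in all subjects before Visit 2.

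- One way is to calculate eGFR for every subject from the screening creatinine and demography, naming the equation and saying whether the laboratory or the site calculates it.
- Resolve the conflict between will and may, and move the eGFR note from urinalysis to chemistry if a creatinine-based value is meant.
- Record the screening eGFR so that a value below the threshold produces an eligibility deviation that the SAP Section 6.3 rule can pick up.
- If the sponsor meant the exclusion to cover documented disease only, the criterion's wording has to say so. That clinical choice is the sponsor's.
- Check the unit printed in [12], which is per m² without the 1.73 reference area. This is editorial.

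Cost: wording changes to both documents and one derived variable. No extra sample or visit is needed. A few more screen failures are possible.

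If enrolment has already begun, the same calculation can be run on stored screening creatinine and the result reported.
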